1 INTRODUCTION

This document describes the statistical analyses for protocol CD-IA-MEDI-551-1155, A Double-masked, Placebo-controlled Study with Open-label Period (OLP) to Evaluate the Efficacy and Safety of MEDI-551 in Adult Subjects with Neuromyelitis Optica and Neuromyelitis Optica Spectrum Disorders.

The scope of this plan includes the primary, interim, and final analyses unless otherwise specified.

2 STUDY OVERVIEW

2.1 Study Objectives

2.1.1 Primary Objective

To compare the efficacy of MEDI-551 versus placebo in reducing the risk of a neuromyelitis optica/neuromyelitis optica spectrum disorders (NMO/NMOSD) attack in subjects with NMO/NMOSD.

2.1.2 Secondary Objectives

1. To compare the efficacy of MEDI-551 versus placebo on the reduction of Expanded Disability Status Scale (EDSS) worsening in subjects with NMO/NMOSD.
2. To compare the efficacy of MEDI-551 versus placebo on the change from baseline of low-contrast visual acuity score in subjects with NMO/NMOSD.
3. To compare the efficacy of MEDI-551 versus placebo in reducing the cumulative active MRI lesion count (new gadolinium [Gd]-enhancing or new/enlarging T2).
4. To compare the efficacy of MEDI-551 versus placebo in reducing NMO/NMOSD-related in-patient hospitalizations in subjects with NMO/NMOSD.
5. To characterize the long-term efficacy of MEDI-551 by means of annualized attack rate.
6. To evaluate the safety and tolerability of a single course of MEDI-551 in the Randomized-controlled Period (RCP) and repeated doses of MEDI-551 in the Open-label Period (OLP).
7. To characterize the pharmacokinetic (PK) profile and immunogenicity of MEDI-551 in NMO/NMOSD subjects.

2.1.3 Exploratory Objectives

1. To compare the effect of MEDI-551 versus placebo on health-related quality of life (HRQoL) as measured by the 4-week recall Short Form-36 (SF-36) Health Survey physical component score (PCS) and mental component score (MCS) in subjects with NMO/NMOSD.

2. To compare the effect of MEDI-551 versus placebo on pain as measured using the pain numeric rating scale (NRS).
3. To characterize the pharmacodynamic (PD) profile (B cells and plasma cell signature) of MEDI-551 in subjects with NMO/NMOSD.
4. To compare the effect of MEDI-551 versus placebo on aquaporin-4-antibody (AQP4-IgG) titer.
5. To compare the effect of MEDI-551 versus placebo on soluble biomarkers (eg, cytokines, chemokines, and immunoglobulins) and genomic (ribonucleic acid [RNA, microRNA]) biomarkers and other relevant cells (eg, T cells, astrocytes) in subjects with NMO/NMOSD.

2.2 Study Design

2.2.1 Overview

This is a multicenter, multinational, randomized, double-masked, placebo-controlled study with an open-label extension period to evaluate the efficacy and safety of intravenous (IV) MEDI-551 in adult subjects with AQP4-IgG seropositive and seronegative NMO and NMOSD. Following a screening period of up to 28 days, 252 subjects with NMO/NMOSD will be randomized in a 3:1 ratio (stratified by AQP4-IgG serostatus and Japan vs non-Japan origin) to receive IV MEDI-551 (300 mg at Day 1 and 300 mg at Day 15) or placebo for a period of 197 days (RCP).

Enrollment of subjects into the study will stop when a total of 67 AC-determined NMOSD attacks occur, when 252 subjects have been randomized, or following a recommendation by the independent Data Monitoring Committee (DMC) to stop enrollment, whichever occurs first.

Subjects who complete the RCP without experiencing an Adjudication Committee (AC)-determined NMO/NMOSD attack will be given the option to enroll into an OLP and will initiate or continue treatment with MEDI-551. Subjects who experience an AC-determined NMO/NMOSD attack during the RCP will be given the option to enroll into the OLP following rescue therapy. Subjects for whom the NMO/NMOSD attack is not determined by the AC will continue in the RCP until Day 197 (or until an AC-determined attack occurs). Subjects who are in the RCP when a total of 67 AC-determined NMOSD attacks have occurred or subjects who are in the RCP when enrollment is discontinued upon recommendation of the independent DMC based on evidence of efficacy and safety, will discontinue the RCP as soon as possible, preferably within 14 days and be given the option to enroll into the OLP.

The OLP will continue for a minimum of 1 year and a maximum of 3 years after the last subject enters the OLP, or until regulatory approval for MEDI-551 in the participating country, or until the Sponsor discontinues development of MEDI-551 in this indication, whichever occurs first. Subjects can choose to exit the OLP at any time at which point they enter the Safety Follow-up Period (SFP; unless consent is withdrawn).

All subjects will continue in the SFP to evaluate the long-term safety of the investigational product (IP).

2.2.1.1 Screening Period

Subjects with the diagnosis of NMO/NMOSD will be screened over a 28-day period to establish their eligibility to participate in the study based on the inclusion and exclusion criteria. AQP4-IgG serostatus will be determined by a central laboratory. For subjects that are found to be AQP4-IgG negative in the screening period, relevant data documenting their NMO disease will be assessed by an independent Eligibility Committee to assure that the data are consistent with the diagnosis of NMO. All subjects that fulfill eligibility criteria will then be randomized into the study; however, subjects undergoing screening at the time when the 252nd subject is randomized and dosed, subjects in screening at the time the 67th AC-determined attack is confirmed, and subjects undergoing screening at the time enrollment is terminated for any other reason, will not be randomized.

2.2.1.2 Randomization (Day 1)

Two hundred and fifty-two subjects will be randomized into the study in a 3:1 ratio to receive IV MEDI-551 or placebo. Randomization will occur on Day 1 (within 28 days of the start of screening) and will be stratified by AQP4-IgG serostatus determined by a central laboratory (in a ratio of approximately 80:20 seropositive and seronegative subjects, respectively), and by region (Japan vs non-Japan).

2.2.1.3 Randomized-controlled Period (Day 1 to Day 197)

Following randomization on Day 1, subjects will be treated with 300 mg MEDI-551 or placebo on Day 1 and Day 15. An oral corticosteroid course will be initiated on Day 1 (prednisone 20 mg/day or equivalent oral glucocorticoid) and will continue until Day 14. Tapering the oral corticosteroids will occur from Day 15 to Day 21. By Day 21, tapering must be completed.

During the RCP, subjects will be followed at scheduled study visits and by telephone interview. The planned duration of the RCP for each subject will be 197 days. All subjects completing the RCP without developing an AC-determined NMO/NMOSD attack will be

given the option to enter the OLP. Subjects who are in the RCP when a total of 67 AC-determined NMOSD attacks have occurred ,or subjects who are in the RCP when enrollment is discontinued upon recommendation of the independent DMC based on evidence of efficacy and safety, will discontinue the RCP as soon as possible, preferably within 14 days and be given the option to enroll into the OLP.

Subjects will be monitored for new or worsening symptoms related to NMO/NMOSD during scheduled study visits and with follow-up phone calls every 2 weeks between study visits (or if a scheduled visit is missed).

When a possible new or worsening symptom(s) related to NMO/NMOSD is identified, subjects will be required to inform the site. If an Assessment Visit is deemed necessary, this must be scheduled as soon as possible but within 72 hours of reporting of the symptoms to the site. At the Assessment Visit, subjects will initially undergo evaluations to determine if the symptoms are related to NMO/NMOSD; if related, the subjects will undergo further evaluations to determine if the symptoms meet at least ONE of the protocol-defined criteria for an NMO/NMOSD attack. In cases where a new or worsening symptom(s) does not meet at least one of the protocol-defined criteria for an NMO/NMOSD attack, the subject will continue in the RCP. The data related to the assessment of the symptoms that were determined by the investigator as not related to NMO/NMOSD will be sent to the AC for review.

Assessment of new symptoms or worsening of existing symptoms should be completed within 5 days to determine if an attack has occurred. Treatment of an attack should preferably be initiated after completion of the attack assessment and the determination that the protocol attack criteria have been met. However, the Principal Investigator can initiate rescue therapy at any time before full assessment is completed. Rescue therapy will be given as directed by the investigator. This may include IV corticosteroids, intravenous immunoglobulin, and/or plasma exchange.

Upon completion of the Assessment Visit, the complete set of data generated from the assessments will be sent to the AC regardless of whether an NMO/NMOSD attack was diagnosed according to the protocol criteria by the Principal Investigator. The adjudication process will be completed within 14 days (+ 3 days) from initiation of the Assessment Visit and the AC determination will be communicated to the Principal Investigator.

Subjects for whom the diagnosis of an NMO/NMOSD attack is not determined by the AC will be given the option to continue in the RCP until Day 197. Subjects for whom the

diagnosis of an NMO/NMOSD attack is determined by the AC will be given the option to enter the OLP.

In addition, subjects who experience an NMO/NMOSD attack that requires rescue treatment and meets the protocol-defined criteria, regardless of the outcome of the AC review, will undergo an Attack Follow-up Visit 28 days from Day 1 of the Assessment Visit. This visit may correspond with an OLP or SFP visit or may be scheduled separately.

If subjects do not wish to enter the OLP or leave the RCP at any point, they will continue to the SFP (unless consent is withdrawn).

2.2.1.4 Open-label Period

Subjects will be given the option to enter the OLP if they:

1. Complete 197 days of the RCP, or
2. Experience an AC-determined NMO/NMOSD attack during the RCP, or
3. Are in the RCP at the time when 67 AC-determined attacks have occurred, or
4. Are in the RCP at the time the Sponsor discontinues enrollment upon recommendation of the independent DMC based on evidence of efficacy and safety.

Subjects who discontinue the RCP for reasons other than an adjudicated NMO/NMOSD attack or the occurrence of 67 AC-determined attacks will not be eligible for the OLP. Reasons for subjects not entering the OLP will be captured. These subjects will be followed for safety in the SFP.

The first day of the OLP will be Day 1 (OLP Day 1). Upon entering the OLP for one of the three reasons outlined above, subjects will receive MEDI-551 as described in Figure 2.3-1. During the OLP, subjects will be followed at scheduled study visits and will continue on MEDI-551 therapy. The OLP will continue for a maximum of 3 years (after the last subject enters), until regulatory approval for MEDI-551 in each participating country or until the Sponsor discontinues development of MEDI-551 in this indication, whichever occurs first. Subjects can choose to exit the OLP at any time for any reason, including seeking alternative treatment options, at which point they enter the SFP (unless consent is withdrawn).

Subjects will be followed for NMO/NMOSD attacks in the same fashion as in the RCP and events will be centrally adjudicated.

2.2.1.5 Safety Follow-up Period

The SFP will start when a subject prematurely discontinues from the RCP or OLP. The length of the SFP will be determined by the time elapsed from the time of the last dose of the investigational product to the time of the premature discontinuation, to complete a total of 52 weeks. During the SFP, the subject will be monitored for AEs/serious adverse events (SAEs), B-cell levels, ADAs, and immunoglobulin levels.

During the SFP, a subject may receive standard treatment for their NMO/NMOSD at the discretion of the investigator.

2.3 Treatment Assignment and Masking

Randomized-controlled Period

Prior to randomization, subjects will be stratified based on AQP4-IgG serostatus (determined at screening) and region (Japan vs non-Japan). Within each stratum, subjects will be randomized in a 3:1 ratio to receive either MEDI-551 300 mg or placebo at Day 1 and 15.

[figure not shown]

Figure 2.3-1 Study Flow Diagram

AC = Adjudication Committee; AQP4-IgG = aquaporine-4 immunoglobulin G; FU = follow-up; IV = intravenous; max = maximum; min = minimum; NMO/NMOSD = neuromyelitis optica/neuromyelitis optica spectrum disorders; OLP = Open-label Period; RCP = Randomized-controlled Period; Q26W = every 26 weeks; SFP = Safety Follow-up Period; yr = year

Open-label Period

All eligible subjects will receive open-label MEDI-551 300 mg every 26 weeks. However, subjects randomized to placebo during the RCP will receive an additional 300 mg MEDI-551 dose at Day 15 of the OLP to maintain a total initial dose of 600 mg. To protect masking, subjects randomized to MEDI-551 during the RCP will receive a placebo infusion at Day 15.

2.4 Sample Size

Study CD-IA-MEDI-551-1155 is being planned to detect a target relative reduction of 60% in risk for time from Day 1 to onset of an adjudicated NMO/NMOSD attack on or before Day 197 with 90% power and $\alpha = 0.05$ (two-sided). A total of 67 AC-determined NMO/NMOSD attacks are required for the ITT population. Subjects will be randomized in a 3:1 ratio to receive either MEDI-551 or placebo within both AQP4-IgG seropositive and seronegative strata. The stratification ratio is anticipated to be approximately 80:20 with higher allocation to the seropositive cohort. If the sero-positive cohort has 80% of the attacks, the study will have approximately 82% power to detect the target relative reduction of 60%.

Two hundred and fifty-two subjects will be randomized. This sample size is based on a blinded review of the attack rate for the first 78 subjects to complete the RCP and on a simulation based on these subjects that indicates a 90% probability of achieving the required 67 AC-determined attacks with 252 subjects.

Within each AQP4-IgG stratum, randomization will also be stratified by region (Japan vs non-Japan). The number of Japanese subjects will be determined primarily by feasibility and will not depend on a minimum number of NMO/NMOSD attacks to be observed from Japanese subjects.

3 STATISTICAL METHODS

3.1 General Considerations

All statistical calculations will be primarily performed using SAS. All data will be presented in the form of listings sorted by treatment and subject number. Tabular summaries will be presented primarily based on the following grouping:

- Stratification: ‘AQP4-IgG seropositive’, ‘AQP4-IgG seronegative’ and ‘All subjects’
 - Treatment: Placebo and MEDI-551 300 mg (nested within each level of stratification)

For pretreatment data (demographics, baseline characteristics, medical/disease history, etc.), an ‘overall’ group combining both treatment groups will also be added to the presentation.

Categorical data will be summarized by the frequency counts and percentage of subjects in each category. Percentages will be calculated based on non-missing observations where applicable. Continuous variables will be summarized by descriptive statistics including number of observations, mean, standard deviation (SD), median, minimum, and maximum. In general, unless stated otherwise, baseline will be defined as the last value prior to first dose of IP. Missing baseline evaluations will not be imputed and will be considered missing.

Unless otherwise stated, all efficacy analyses will be done with a two-sided test at 5% significance level. Where appropriate model based estimates will be presented with their two-sided 95% confidence interval (CI) and p-values. Categorical data analyses using the Pearson chi-square test will be substituted by the Fisher’s exact test if greater than 20% of expected contingency table cell counts are less than 5.

Table 3.1-1 provides an overview of analysis milestones for this study.

Table 3.1-1 Overview of Analysis Milestones

Type of Analysis	Analysis milestones	Data to be analyzed
Unmasked futility analysis	When approximately 34 AC-determined attacks occur are observed (See Section 5)	Cumulative data on attack
Primary analysis	All subjects complete the RCP	All the data (including OLP and SFP) available at the time of database snapshot
Annual update of efficacy and safety	On an annual basis after the primary analysis	Cumulative safety and efficacy data (all study periods)
Final analysis	All subjects complete the SFP (or withdraw)	Cumulative safety and efficacy data

3.1.1 Study Points of Reference

Table 3.1.1-1 provides definition of baseline and study reference days for reporting purposes.

Table 3.1.1-1 Definition of Baseline and Study Day for Analysis Purposes

	RCP	OLP	Any MEDI-551 exposure
Baseline	Baseline is defined as the last non-missing measurement for the endpoint of interest taken before the first dose of IP. In cases where baseline measurements are taken on the same day as IP and no times are reported, it will be assumed that these measurements are taken prior to IP being administered. For subjects who are randomized but not dosed after randomization, the baseline of the study is defined as the last non-missing measurement prior to or on the date of randomization.	No separate Baseline will be defined at entry of Open label period.	For analysis by any MEDI-551 exposure, baseline for Placebo subjects may be redefined as last non-missing value prior to 1 st MEDI-551 administration.
Day 1 of the study period	Day 1 for the RCP is defined as the day of first IP administration and will be denoted as Day 1 (RCP). For subjects who are randomized but not dosed after randomization, Day 1 is defined as the date of randomization.	Day 1 for the OLP is defined as the day of first open-label IP administration and will be denoted by Day 1 (OLP).	Day 1 for the MEDI-551 is defined as the day of first MEDI-551 administration irrespective of RCP or OLP and will be denoted by Day 1 (MEDI-551).
Study day for each period for reporting purpose	RCP Study Day is defined as the number of days from Day 1 (RCP) calculated as follows: = Date of Interest – Date of Day 1 (RCP) (for dates prior to Day 1 (RCP)) = Date of Interest – Date of Day 1 (RCP) + 1 (for dates on or after Day 1 (RCP))	OLP Study Day is defined as the number of days from Day 1 (OLP) calculated as follows: = Date of Interest – Date of Day 1 (OLP) (for dates prior to Day 1 (OLP)) = Date of Interest – Date of Day 1 (OLP) + 1 (for dates on or after Day 1(OLP))	Any MEDI-551 exposure is defined as the number of days from Day 1 (MEDI-551) calculated as follows: = Date of Interest – Date of Day 1 (MEDI-551) (for dates prior to Day 1 (MEDI-551)) = Date of Interest – Date of Day 1 (MEDI-551) + 1 (for dates on or after Day 1(MEDI-551))

3.1.2 Analysis Windows

Since the actual study visit for a subject may not exactly coincide with their targeted visit date, the actual visit date will be mapped to the analysis visit as provided in Table 3.1.2-1 below.

Table 3.1.2-1 Analysis Window for Randomized- controlled Period			
Study Week	Nominal Day	Analysis window	Interval (days)
0	1	---	---
1	8	2-11	10
2	15	12-22	11
4	29	23-43	21
8	57	44-71	28
12	85	72-99	28
16	113	100-134	35
22	155	135-176	42
28	197	177-Day prior to OLP or SFP	---

Different sets of visit windows may be derived for measurements assessed at less frequent visits than shown in Table 3.1.2-1. Similar analysis windows will be created for OLP related analyses. If more than one actual visit falls within the same defined window, the closest visit with non-missing result to the target day will be considered for analysis. If two assessment actual dates are equidistant from the target day, the latter visit will be considered for analysis.

For retest values of lab data, the retest value (the last observation within the same visit day) will be chosen. Analysis windows will be applied after selection of such values.

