4.2.2.2 Open-label Period

Table 7 shows all procedures to be conducted during the OLP. Patient-reported outcomes should be done first followed by all other assessments/procedures in an order determined by the site. For subjects completing Day 197 of the RCP, Day 1 of the OLP should be the same day; however, it may be delayed for up to 14 days (procedures do not need to be repeated). Subjects are not permitted to enter the OLP after 14 days, unless there is a compelling reason that is discussed with, and agreed to by the medical monitor, in which case a short extension may be granted.

Subjects who experience an AC-determined NMO/NMOSD attack during the RCP must enter the OLP within 28 days of the site receiving confirmation of the attack from the AC. Entering subjects into the OLP beyond the 28 days from the AC confirmation should be discussed with the medical monitor. Procedures that were done during the last visit can be used for Day 1 of the OLP if this occurs within 14 days from the Assessment Visit. Otherwise, procedures required for OLP Day 1 should be performed.

Subjects who are in the RCP at the time the 67th AC-determined attack occurs, or when enrollment is discontinued upon recommendation of the independent DMC based on evidence of efficacy and safety, and wish to enroll in the OLP, should do so as soon as possible, preferably within 14 days. Consultation with the medical monitor is advised in cases where the transition to the OLP is not completed within 14 days.

Administration of MEDI-551 will start on OLP Day 1.

The OLP will continue for a minimum of 1 year after the last subject enters and a maximum of 3 years (after the last subject enters), or until regulatory approval for MEDI-551 in the participating country, or until the Sponsor discontinues development of MEDI-551 in this indication, whichever occurs first. All subjects entering the OLP will be required to re-consent prior to receiving MEDI-551. Subjects can choose to exit the OLP at any time, for any reason, including seeking alternative treatment options, at which point they will enter the SFP (unless consent is withdrawn).

If a subject discontinues from the OLP, all procedures should be conducted as presented in Table 7 for the Day 365/EDV. If a subject withdraws from the study, every attempt should be made to have the subject come to the site to conduct EDV assessments. Following the EDV, the subject will enter the SFP (Section 4.2.4).

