3.7.1 Adverse Events

The definitions of TEAE provided in Table 3.7.1-1 will be used for analysis of adverse events based on different study periods. Figure 3.7.1-1 provides a visual representation of TEAEs during different study periods. The AE(RCP), AE(OLP) and AE(SFP) represent TEAEs during RCP, OLP and SFP, respectively.

Table 3.7.1-1 Definition of Treatment-Emergent AEs (TEAEs)

RCP	OLP	SFP	Any MEDI-551 Exposure
For subjects entering the OLP, a TEAE will be defined as any AE with an onset time on or after the first dose of IP in the RCP up to the time prior to the first OLP dose.	A TEAE will be defined as any AE with an onset time on or after 1st dose of OLP up to and including the day prior to the SFP entry.	A TEAE will be defined as any AE with an onset on or after entry to SFP.	A TEAE will be defined as any AE with onset on or after the first MEDI-551 dose (either RCP or OLP) up to and including the day prior to entry to SFP.
For subjects entering the SFP after RCP, a TEAE will be defined as any AE with an onset on or after the first dose of IP in the RCP up to and including the day prior to the entry to SFP.	---		
For subjects not entering the OLP or SFP after RCP, a TEAE will be defined as any AE with an onset on or after the first dose of IP in the RCP			

[figure not shown]

Figure 3.7.1-1 Visual definition of TEAEs during different study periods

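### The SAP's Week 28 window closes the day before the open-label period, so the Day 197 visit of a completer who rolls over on the protocol's default day is not mapped to Week 28

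*SAP*

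**What the plan says.** - **SAP 3.1.2** works on dates: "the actual visit date will be mapped to the analysis visit as provided in Table 3.1.2-1 below". The Week 28 row, nominal Day 197, reads "177-Day prior to OLP or SFP".
- **SAP 3.1.1** fixes the other side of the boundary: "Day 1 for the OLP is defined as the day of first open-label IP administration".
- **Protocol 4.2.2.2** gives the default path: "For subjects completing Day 197 of the RCP, Day 1 of the OLP should be the same day". A delay of up to 14 days is allowed without repeating procedures. Footnote a of Table 7 and Protocol 4.5.1.2 say the same.
- **SAP 3.7.1** draws the boundary differently for adverse events. For subjects who enter the OLP, the RCP runs "up to the time prior to the first OLP dose".
- **SAP 3.1.2** also has a flexibility clause: "Different sets of visit windows may be derived for measurements assessed at less frequent visits than shown in Table 3.1.2-1". It gives no alternative bounds.

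**The concern.** Protocol Table 6 makes Day 197 the last and fullest assessment of the randomized period. On the default path its calendar date is also OLP Day 1, so it lies one day beyond the end of its own window. The completers who follow the schedule are left out of Week 28, and those who enter the OLP late make up the Week 28 column. That column is then a subset selected by timing of OLP entry.

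Week 28 is not a minor time point for drug level and B cells. The dose rationale in Protocol 3.2.2 predicts B-cell suppression for 28 weeks, and these summaries are where a reader would look for it.

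**Working it through.** **1. The table's own figures.** Width = upper − lower + 1 reproduces every stated interval:

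| Nominal day | Window | Computed | Stated |
|---|---|---|---|
| 8 | 2–11 | 10 | 10 |
| 15 | 12–22 | 11 | 11 |
| 29 | 23–43 | 21 | 21 |
| 57 | 44–71 | 28 | 28 |
| 85 | 72–99 | 28 | 28 |
| 113 | 100–134 | 35 | 35 |
| 155 | 135–176 | 42 | 42 |

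Each upper bound is the midpoint to the next nominal day, rounded down; for example (155 + 197)/2 = 176. The fault is confined to the upper end of the last row, which has no stated width.

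**2. The Week 28 rule.** Let v be the day of the Day 197 visit and d the delay to the first open-label dose, so OLP Day 1 = v + d. The visit is captured if 177 ≤ v ≤ v + d − 1. Since v is at least 190, this reduces to d ≥ 1.

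- Inputs: v = 190 to 204 (Table 6 allows ± 7 days) and d = 0 to 14 (Protocol 4.2.2.2), giving 15 × 15 = 225 combinations.
- As written: 15 × 14 = 210 are captured. The 15 lost are exactly those with d = 0. For v = 197 and d = 0 the window is Days 177 to 196.
- With the upper bound moved to the first open-label dose (v ≤ v + d): 225 of 225 are captured.

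**3. What remains for a same-day roll-over.** From Table 6, the last earlier scheduled sample is:

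- PK, B cells and gene expression: Day 155, which is 197 − 155 = 42 days earlier.
- AQP4-IgG titre, ADA, EDSS/FSS and acuity: Day 85, which is 197 − 85 = 112 days earlier.

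Both days belong to their own windows (135–176 and 72–99), so neither fills the Week 28 cell.

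**4. Whether OLP Day 1 replaces the values.** Table 7 schedules no PK, flow cytometry, gene expression, EDSS or acuity on OLP Day 1. ADA, immunoglobulins and titre are listed there, but completers need not repeat them, so the Day 197 sample is the only one. SAP Table 3.1.1-1 assumes that an untimed same-day measurement is pre-dose, but only for baseline.

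**5. Which results use the window.** By-visit summaries are specified for PK (SAP 3.9), for titre, B cells and gene signature, with an ANCOVA of titre change (SAP 3.6.1.2), for one ADA line (SAP 3.8), and for EDSS, functional system scores and visual acuity (SAP Table 3.5.4-1).

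**6. Size.** The share of same-day roll-overs is not in the documents. Purely as an illustration, assume 252 dosed, 67 with an attack and no other dropout: 252 − 67 = 185 attack-free completers.

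| Same-day share (assumed) | Without a Week 28 value | Of 252 |
|---|---|---|
| 25% | about 46 | 18% |
| 50% | about 92 | 37% |
| 75% | about 139 | 55% |
| 100% | 185 | 73% |

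**The case against.** The case against has several parts.

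- **Evident purpose.** A row with nominal Day 197 is plainly meant to hold the Day 197 visit, and a programmer may read it that way. That is likely, but it means departing from the stated bound.
- **Flexibility clause.** Other windows may be set for less frequent measures. This stands in part for EDSS, acuity, ADA and titre, though no bound is given. It cannot cover PK or flow cytometry, which are taken at every Table 6 visit.
- **Nothing is destroyed.** This stands: SAP 3.1 lists all data, so the values are unmapped rather than lost. Most of the affected outputs are descriptive, and no imbalance between arms is shown.
- **The main tests bypass the table.** This stands. Primary censoring is at the Day 197/discontinuation visit itself (SAP 3.4.1.3). The pain ANCOVA and the mRS analysis use the last RCP value (SAP 3.5.1.1 and 3.5.3).

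Three stronger readings are tempting and are not supported.

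- **Key secondary data are lost.** SAP 3.4.2.1 defines EDSS worsening and acuity change at the last RCP visit and MRI lesions cumulatively over the RCP, not by this window. Protocol 3.1.1.3 gives the RCP a planned 197 days, so the Day 197 visit belongs to it.
- **Missing EDSS would be counted as worsening.** Even under the day-before cut a Day 85 EDSS would normally remain, so nothing in the documents leads from the window to that imputation.
- **The Week 1 to 22 rows also need a stop at OLP entry.** The table is titled for the RCP, and SAP 3.1.2 promises separate OLP windows.

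**Conclusion.** The concern holds for by-visit Week 28 results. The rule as stated is wrong, not merely silent: it excludes the on-schedule Day 197 visit and retains only delayed roll-overs. PK and B cells are affected without qualification; the sparser measures are affected unless other windows are written.

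The primary analysis is untouched. The key secondary endpoints would be reached only if the day-before cut were also taken as the end of the RCP. The SAP does not say that, but it does not settle it either. Person-years (Table 3.3.3-1) stop the day before the OLP, while concomitant medications (3.3.4.1) and treatment-emergent events run to the first open-label dose. Under the day-before cut, EDSS and acuity would fall back to Day 85, and attack-free completers would have no scheduled post-baseline RCP scan.

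The conclusion rests on reading the row literally and on the protocol's same-day default for completers. Subjects moved across after the 67th attack or the DMC recommendation follow a different timing rule, for which same-day entry is not stated. The number of subjects affected cannot be derived from the documents.

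**What to change.** In SAP Table 3.1.2-1, let the Week 28 row run from Day 177 to the first open-label dose, including assessments made on OLP Day 1 before that dose. For subjects who do not enter the OLP, let it run through the Day 197/EDV visit inclusive.

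Add that same-day assessments without a recorded time count as pre-dose, as Table 3.1.1-1 already does for baseline. State that this same boundary defines the last visit during the RCP, so the key secondary endpoints do not depend on a programming choice.

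The cost is one table row and two sentences, with no new data. The boundary is the one the SAP already uses for treatment-emergent events. It should be settled before unmasking.
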